5.4.2 Secondary Efficacy Endpoints

The analyses of secondary efficacy endpoints will be performed for the main treatment period only.

The number and percent of weeks of platelet counts will based on the number of scheduled weekly platelet assessments (i.e., not by study day) and only weeks with non-missing platelet counts will be included in the calculations.

5.4.2.1 Percent of weeks with platelet counts \geq 50,000/ μ L by dose level and overall

The percent of weeks that patients achieve platelet counts \geq 50,000/ μ L in the main treatment period will be summarized across all dose levels. This table will be repeated by starting dose.

5.4.2.2 Proportion of patients with at least 4 out of the final 8 platelet counts \geq 50,000/ μ L across all dose levels

The final 8 scheduled platelet counts are the measurements performed in the last 8 weeks of study treatment (depending on treatment duration, not necessarily from Week 17 to Week 24) in the main treatment period and including missing result(s). The number and percentage of patients who had at least 4 out of the final 8 platelet counts $\geq 50,000/\mu L$ will be tabulated across all dose levels. Patients with less than 4 platelet counts will be considered as non-responders. A 95% confidence interval will be calculated for the proportions using the Clopper-Pearson method. This summary will be repeated by Starting Dose.

As a sensitivity analysis, this endpoint will be repeated for patients who completed 24 weeks of main treatment where the final 8 scheduled platelet counts are the measurements performed from Week 17 to Week 24.

In addition, this endpoint will be analyzed for patients starting rilzabrutinib 400 BID where the final 8 scheduled platelet counts are the measurements performed from Week 17 to Week 24.

5.4.2.3 Change from baseline to the average of the post Day 1 platelet counts by dose level and overall for patients had > 4 weeks of study drug on that given dose level

The change from baseline to the average of the post Day 1 platelet counts by dose level and overall will be summarized by descriptive statistics for the observed values collected in the main treatment period for patients who had more than 4 weeks of study drug on that given dose level. The number of weeks of study drug will be determined by number of on-study drug visits, eg, Patients who attended Cycle 1 Day 1 and did not discontinue study drug on or before data of Cycle 2 Day 1 visits will be included.

5.4.2.4 Number of weeks with platelet counts \geq 50,000/ μ L across all dose levels

The number of weeks that patients achieved platelet counts $\geq 50,000/\mu L$ in the main treatment period will be summarized across all dose levels. Summaries will be repeated in these 2 groups of patients: those that intended to finish the study drug at 12 weeks, i.e., patients who enrolled under protocol version v7.0and those that intended to finish at 24 weeks, i.e., patients who enrolled under protocol version 8.0 and up. This table will be repeated by Starting Dose.

5.4.2.5 Number of weeks with platelet counts \geq 30,000/ μ L across all dose levels

The number of weeks that patients achieved platelet counts \geq 30,000/ μ L in the main treatment period will be summarized across all dose levels. Summaries will be repeated in these 2 groups of patients: those that intended to finish the study drug at 12 weeks, i.e., patients who enrolled under protocol version v7.0 and those that intended to finish at 24 weeks i.e., patients who enrolled under protocol version 8.0 and up. This table will be repeated by Starting Dose.

5.4.2.6 Time to first platelet count \geq 50,000/ μ L across all dose levels

Time to first platelet count ≥ 50,000/μL during the main treatment period in days will be calculated as:

(Date of first occurrence of platelet count ≥ 50,000/μL – Date of first study drug dosing) +1

[figure not shown]
Patients who did not experiencing platelet count ≥ 50,000/µL will be censored

[figure not shown]
- at the end of the main on-treatment period for those who completed the main treatment period,
- at Week 25 (ie, 1 week after the protocol scheduled Week 24 visit) for those who prematurely discontinued the main treatment due to any AE or lack of response, and
- at the time of discontinuation for those who prematurely discontinued the main treatment due to other reasons.

[figure not shown]
All platelet counts including unscheduled measurements will be included. The number of days to first platelet count $\geq 50,000/\mu$ L will be summarized by descriptive statistics for overall across all dose levels.

Kaplan-Meier estimates will be calculated for time to first platelet \geq 50,000/ μ L. The 25%, median and 75% time to event will be produced with the corresponding 2-sided 95% confidence intervals. Kaplan-Meier plot will also be provided.

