5.4 Efficacy Analyses

The ITT population will be used for all efficacy analyses. For analyses of a particular study drug dose level, all patients who received that dose at least once will be included.

Rescue medication is defined as any therapy used to rescue a patient (one of intravenous immunoglobulin [IVIG], high-dose steroids, platelet infusion or anti-D immunoglobulin infusion). A rescue therapy may be used if there is a significant safety event requiring 'rescue' from a deterioration in the patient's platelet count that in the opinion of the investigator puts the patient at significant risk of a safety event. Patients who take rescue while on study will be discontinued. Response status for patients who receive rescue therapy while on study will be evaluated using the platelet counts up until the time of rescue therapy.

The descriptive statistics for the main treatment period will be done by starting dose and overall for all study visits and by cycle of exposure (as appropriate), unless specified otherwise. All binomial confidence intervals for efficacy analyses will use the Clopper-Pearson method. Descriptive summary will be generated for data collected during the LTE period as needed. Patient data listings will be listed

by starting dose, patient, dose level and study visit, including both of the main treatment period and LTE period.

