4.3.2 Main analytical approach

The responder of the primary endpoint must have met ALL of the following criteria:

 Platelet counts ≥ 50,000/µL for at least 8 out of the last 12 weeks [Week 14 (Day 92) to Week 25 (Day 169)] during the 24-week treatment period (or equivalently the ontreatment period for efficacy).

The on-treatment period for efficacy is defined as the period from the date of the 1st IMP administration

- up to 1 day after the last IMP administration for participants who did not enter LTE, or
- Week 25 (Day 169) visit for participants who entered LTE.

The on-treatment period for efficacy will be used for all efficacy analyses related to platelet counts.

And,

- Not rescued after 10 weeks of treatment. "Rescued after 10 weeks of treatment" for efficacy analysis is defined as from Week 11 (Day 71) to the day prior to the last date of IMP administration for those do not enter LTE or the visit date of Week 25/C1D1_LTE (Day 169) for those entered LTE.
- Not discontinued before Week 25 due to related TEAE (per investigator's assessment), lack of response, or need to rescue medication as recorded in eCRF, i.e., participants who discontinue before Week 25 and the discontinuation reasons are treatment related adverse event (AE), lack of response, or need of rescue medication will be considered as non-responders.

The response rate will be summarized for ITT population along with the 95% exact Clopper-Pearson Confidence Interval (CI).

Platelet counts and the change from baseline will be summarized by visit. The time course of platelet count will be described graphically, and the following plots will also be provided:

- Individual platelet count profile: line plot of platelet count by visit for each participant
- Spaghetti plot platelet count by participant in each study period (i.e., main and LTE)
- Median platelet count/change from baseline by visit in each study period

Property of the Sanofi group - strictly confidential

28-Nov-2022 Version number: 1

An unscheduled platelet count will be allocated to a scheduled visit if it is within the visit window of the scheduled visit where a platelet count is not available (see Section 5.3).

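### Part A's 4-of-final-8 platelet endpoint has no non-responder rule for early treatment failure, so a patient withdrawn soon after losing response can count as a responder

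*SAP*

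**What the plan says.** SAP Part A 5.4.2.2 takes the final 8 scheduled counts from the last 8 weeks of main treatment that the patient actually received, "depending on treatment duration, not necessarily from Week 17 to Week 24", with missing results kept among the 8. The quantity reported is "The number and percentage of patients who had at least 4 out of the final 8 platelet counts" at or above 50,000/µL, with a 95% Clopper-Pearson interval, overall and by starting dose. One failure rule is given: "Patients with less than 4 platelet counts will be considered as non-responders".

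Three statements in SAP Part A 5.4 complete the rule:

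- "The ITT population will be used for all efficacy analyses", so early leavers are included.
- Use of rescue during the study ends the patient's participation.
- "Response status for patients who receive rescue therapy while on study will be evaluated using the platelet counts up until the time of rescue therapy".

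Section 5.4.2.2 adds two analyses with the window fixed at Weeks 17 to 24. One is a sensitivity analysis restricted to patients who completed 24 weeks. The other covers patients who started at 400 mg BID and is not restricted to completers.

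Two other endpoints do use the reason for stopping. For time to first count of at least 50,000/µL (SAP Part A 5.4.2.6), patients without an event who leave for any AE or lack of response are censored at Week 25 rather than when they leave. For the Part B primary endpoint (SAP Part B 4.3.2), patients who stop before Week 25 for a treatment-related AE, "lack of response, or need of rescue medication will be considered as non-responders".

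**The concern.** The endpoint will be read as response at the end of treatment. For a patient who completes the planned course, the last 8 treated weeks are the right weeks. For a patient who stops because treatment failed, the window moves back to weeks that may still hold good counts, and the failure itself is not scored.

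The protocol foresees this course of events. Its Part A dose escalation rules (Section 4.4) describe a platelet response that proves transient, then rescue, then discontinuation.

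If such patients count as responders, the ITT rate overstates end-of-treatment response, and it is not comparable with a Part B rate that scores them as failures.

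**Working it through.** **Plan's own figure.** No precision or expected rate is stated for this endpoint. The only Part A figure (protocol Section 10.5) concerns the primary endpoint: 40% expected, n = 15, 80% confidence. It reproduces: 1.2816 × √(0.4 × 0.6 / 15) = 0.162, so the lower limit is 40% − 16.2% = 23.8%, stated as 24%. It does not bear on this point.

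**Step 1: what the rule allows.** Suppose a patient has g consecutive weekly counts at or above 50,000/µL, then k low weeks, then stops. The number of good counts in the last 8 treated weeks is at least min(g, 8 − k). The patient is a responder whenever g ≥ 4 and k ≤ 4.

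**Step 2: constructed patients** (weekly counts in thousands/µL; invented to test the rule, not trial data).

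| Course | Counts in last 8 treated weeks | Score | Section 5.4.2.2 rule | Fixed Weeks 17–24 |
|---|---|---|---|---|
| A. Rescued at Week 8 | 55, 62, 58, 51, 34, 22, 14, 9 | 4 of 8 | responder | non-responder |
| B. Stops for an AE after 4 counts | 52, 60, 66, 71 | 4 of 4 | responder | non-responder |
| C. Stops for lack of response at Week 12 | 52, 55, 58, 51, 44, 30, 22, 18 | 4 of 8 | responder | non-responder |
| D. 60 through Week 16, then 20; stays to Week 24 | 20 in all eight | 0 of 8 | non-responder | non-responder |
| E. Same as D, but withdrawn after Week 20 | 60 in four, 20 in four | 4 of 8 | responder | non-responder |

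D and E lose response in the same week. The one who stays is a failure and the one who is withdrawn is a success. A, B and C have no counts in Weeks 17 to 24, so they fail the fixed window through the fewer-than-4 rule. E has four counts there, none of them good.

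**Step 3: size.** N = 60 is the approximate enrolment in SAP Part A 2.3. Each misclassified patient adds 1/60 = 1.7 percentage points. How many there are is not given, so the numbers below are assumptions: 18 responders when early failures count as non-responders, plus 0 to 9 misclassified patients (95% Clopper-Pearson intervals).

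| Misclassified (assumed) | Rate | 95% CI |
|---|---|---|
| 0 | 18/60 = 30.0% | 18.8 to 43.2 |
| 3 | 21/60 = 35.0% | 23.1 to 48.4 |
| 6 | 24/60 = 40.0% | 27.6 to 53.5 |
| 9 | 27/60 = 45.0% | 32.1 to 58.4 |

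**Step 4: do the added analyses repair it?** In the completers-only analysis the early failures leave the denominator. If the same 18 responders are all completers, the rate is 18/50 = 36%, 18/40 = 45% or 18/30 = 60% with 50, 40 or 30 completers, against 30% of 60. The fixed-window analysis of 400 mg BID starters does score early failures as non-responders, provided the fewer-than-4 rule applies there too, but it says nothing about the other starting doses or the overall rate.

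**The case against.** The best defence has four parts.

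- **The window has a reason.** Planned treatment was 12 weeks under protocol version 7.0 and 24 weeks or more from version 8.0, and the protocol itself defines the endpoint by the final 8 counts. This stands. It justifies a moving window for patients who complete their plan, but not for those who stop early because of failure.
- **The selected dose is already covered.** The Week 17 to 24 analysis of 400 mg BID starters applies nearly the handling asked for here. This stands, with the proviso on the fewer-than-4 rule, and confines the point to the overall rate and the other starting doses.
- **A reader could divide the completers' responders by the ITT number.** This is only a partial workaround. It fails every version 7.0 patient, whose plan ended at 12 weeks, and no such table is planned.
- **The consequence is limited.** This is one of six secondary endpoints, all descriptive, with no hypothesis testing (SAP Part A 3.8). Individual platelet profiles and rescue tables would make the cases visible. This stands, although the reported rate and its interval would be unchanged.

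Several stronger readings are tempting and not supported. A reader might take Part B as precedent for failing anyone who stops for any AE; its rule covers treatment-related events only. A reader might think that a patient treated for only 4 weeks can lose response and still succeed; with 4 counts all must be good, so course B is someone who stopped for another reason, and how to score that person is a choice of estimand. Course C is possible but likely to be uncommon: half of the last 8 weekly counts at or above 50,000/µL is enough to meet the platelet criterion for the extension. Part B's own 4-of-last-8 endpoint mentions 24-week completion, but its wording can be read as a condition on responders or a restriction of the denominator, so it settles nothing.

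**Conclusion.** The gap is real and follows from the text. For this endpoint nothing makes a patient who stops early through treatment failure a non-responder, and the rescue rule in SAP Part A 5.4 confirms that rescued patients are scored on their earlier counts. Judging up to rescue suits the primary endpoint, which asks whether a response was ever achieved; it does not suit an end-of-treatment rate.

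The direction is certain: compared with a rule that fails these patients, the rate can only be higher or equal. The amount is not. It is 1.7 points per patient at N = 60, for a number of patients that the documents do not give and that may be zero. The route is most plausible for abrupt loss of response followed by rescue. The documents do not support saying that the rate is inflated by any particular amount, or that the 400 mg BID starting-dose result is compromised. The rule should be changed; no test result depends on it.

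**What to change.** In SAP Part A 5.4.2.2:

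- Keep the sliding window for patients who complete their planned main treatment (12 weeks under version 7.0; 24 weeks or more from version 8.0).
- In the ITT analysis, count patients who stop before their planned end for lack of response, need of rescue or a treatment-related AE as non-responders, in line with the Part B primary endpoint. If any AE is used instead, as in SAP Part A 5.4.2.6, say so and note that this is stricter than Part B.
- State that the fewer-than-4 rule also applies to the Week 17 to 24 analysis of 400 mg BID starters.
- Report the present rule as a sensitivity analysis.

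The cost is a sentence or two and one re-run table from data already collected. SAP Part B 1.1 says that a Part A study report has been prepared, so the change would now be a clearly labelled additional tabulation. The downside is that the rate may become slightly less favourable.

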			On-treatment clinic visits, treatment cycles of 28days, X≤6 ¹⁶					Early
	Screening (D-28 to D-1)	C1D1 only	CXD1 (first day of each cycle) ¹³	CXD15	D169 (last day of active rilzabrutinib (PRN1008) treatment)	End of Study D197	Weekly lab visit between clinic visits ¹⁴	Withdrawal/ Unscheduled visit
	,	,	,,,,,		,			
ITP-BAT Bleeding Scale ¹²	Х		X	Х	X	Х		X

- 1. Clinic/laboratory visit windows are ± 3 days for all dosing period and lab visits. Labs to confirm eligibility prior to Cycle 1 Day 1 may be taken up to 3 days in advance of Cycle 1 Day 1.
- 2. See protocol section 4.3 of the protocol dose-escalation rules
- 3. Full physical examination at screening, abbreviated physical examination at other visits.
- 4. Triplicate ECG pre-dose and at 2 hours post-dose (± 15 minutes) on the first day of dosing at each new dose level. Where patients are continuing into a new cycle at the prior dose level, ECG is not required.
- 5. For women of childbearing potential only. Serum pregnancy tests are performed at screening, urine pregnancy tests are performed at other visits.
- 6. To confirm postmenopausal status for women who are not surgically sterile and of reproductive potential
- 7. T/B/NK/monocyte counts (i.e., CD3, CD4, CD8, CD14, CD19, CD16/56), and B cell subsets (i.e., naïve, memory and plasmablasts)
- 10. On Day 1 of each new dose level cycle, patients will take their dose in the clinic and remain in the clinic for intensive PK sampling for 6 hours following the first dose at time points: 0, 0.5, 1, 1.5, 2 (time windows for first 2 hours are ± 2 minutes), 3, 4, and 6 hr (time windows for > 2 hr samples are ±5 minutes). On subsequent clinic visits of each dosing cycle, patient should take their dose in the morning before the clinic visit (whether dosing is QD or BID), and the PK sample is taken at random times after last dose (with time of last dose recorded on CRF, no time window). Where patients are continuing into a new cycle at the prior dose level, PK sampling is not required.
- 11. If still taking rilzabrutinib (PRN1008)
- 12. ITP-BAT scale performed at all clinic visits but not laboratory-only visits
- 13. Assessments on Day 1 of each 28-day treatment Cycle are performed pre-dose; ECGs and PK samples are also collected at additional times post-dose per Footnote 4 (ECGs) and Footnote 10 (PK samples).

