3.3 Treatment Groups

3.3.1 Treatment Group Labels

The following treatment group labels will be used in the tables, listings and figures:

Treatment Group Label	Patients Included
Overall	All patients in the population will be included in this group.
Starting Dose 200 mg QD	Patients will be classified to these groups according to the starting
Starting Dose 400 mg QD	dose received. Each patient will be assigned to only one of these
Starting Dose 300 mg BID	groups.
Starting Dose 400 mg BID	
200 mg QD	Patients are evaluable in the dose group(s) if the dose level was
400 mg QD	received during the defined period (Sections 3.4.1and 3.5.2). Since
300 mg BID	most patients received more than one dose, a given patient can be
400 mg BID	assigned to multiple dose levels.
	For each of the following type of analyses, patients will be classified to
	each dose level based on:

Treatment Group Label	Patients Included
	 Dose level received prior to the visit for responder analyses, time-to analyses and analyses of proportion of patients meeting an endpoint, i.e., percent of weeks with platelet counts ≥ 50,000/μL. Dose level received at the onset of event for adverse events, and bleeding events analyses. Adverse events started after date of last dose of study drug will be attributed to the last dose level received. Dose level received during the time the medication was taken for any medication analyses. Medications taken after date of last dose of study drug will be attributed to the last dose level received.

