3.4.4 Analysis Visits

In addition to study visits described above, analysis visits based on dosing cycle of each dose level will be derived for descriptive summary during the main treatment period as follows:

- 1st Cycle of Exposure: Day 1, Day 8, Day 15 and Day 22
- 2nd Cycle of Exposure: Day 1, Day 8, Day 15 and Day 22
- 3rd Cycle of Exposure: Day 1, Day 8, Day 15 and Day 22
- 4th Cycle of Exposure: Day 1, Day 8, Day 15 and Day 22
- 5th Cycle of Exposure: Day 1, Day 8, Day 15 and Day 22
- 6th Cycle of Exposure: Day 1, Day 8, Day 15 and Day 22
- Xth Cycle of Exposure: Day 1, Day 8, Day 15 and Day 22 for patients who had treatment cycle(s) beyond Cycle 6
- Last value on-treatment (Last post-baseline visit during the main on-treatment period including unscheduled visits within each dose level)

For example, if a patient received 200 mg QD at Cycle 1, 400 mg QD at Cycle 2 and Cycle 3 and 300 mg BID at Cycle 4 and Cycle 5, the scheduled visits will be mapped to the analysis visits as follows:

Dose Level	Scheduled Visit	Analysis Visit
200 mg QD	Cycle 1 – Day 1, 8, 15 and 22	200 mg QD: 1st Cycle of Exposure – Day 1, 8, 15 and 22
400 mg QD	Cycle 2 – Day 1, 8, 15 and 22	400 mg QD: 1st Cycle of Exposure – Day 1, 8, 15 and 22
400 mg QD	Cycle 3 – Day 1, 8, 15 and 22	400 mg QD: 2 nd Cycle of Exposure – Day 1, 8, 15 and 22
300 mg BID	Cycle 4 – Day 1, 8, 15 and 22	300 mg BID: 1 st Cycle of Exposure – Day 1, 8, 15 and 22
300 mg BID	Cycle 5 – Day 1, 8, 15 and 22	300 mg BID: 2 nd Cycle of Exposure – Day 1, 8, 15 and 22

Note: Visits occurred at and after the visit where dose reduction occurred will not be mapped.

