5.3.2 Actual Total Cumulative Dose (mg)

Actual total cumulative dose in main treatment period (mg) = Sum of (Dose Level $_i$ (x2 if BID) x actual duration of study drug exposure in main treatment period for Dose Level $_i$ – total # of doses missed in Dose Level $_i$ during main treatment period))

Actual duration of study drug exposure in main treatment period for each dose level will be based on (Date of last dose in Dose Level $_i$ – Date of first dose in Dose Level $_i$) + 1, regardless of unplanned intermittent interruption

For patients who only had one dose level, the actual duration of Dose Level_i is the same as duration of study drug exposure in Section 5.3.1.

For patients with more than one dose levels:

- Date of first dose for the starting dose level is date of first dose taken at Cycle 1 Day 1.
- Date of first dose for the subsequence dose levels is the date of dosing reported on the Study Drug Administration eCRF where a dose adjustment was made. If the date of dosing is missing, then the date of visit where dose adjustment made will be used.
- Date of last dose for Dose Level_i is the date of first dose of the next dose level -1.
- Date of last dose for the last dose level is the date of last dose reported on the End of Study form.

Actual total cumulative dose in LTE treatment period (mg) = 400 mg x2 if BID x actual duration of study drug exposure in LTE treatment period – total # of doses missed in LTE treatment period)

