5.4.1 Primary Efficacy Endpoint

Platelet count is measured at visits as specified in the Schedule of Assessments (Table 3 to Table 6).

The primary efficacy endpoint is:

 Proportion of patients able to achieve two or more consecutive platelet counts, separated by at least 5 days, of ≥ 50,000/µL AND an increase of platelet count of ≥ 20,000/µL from baseline, by dose level, without use of rescue medication in the 4 weeks prior to the latest elevated platelet count.

The number and percentage of patients who meet the primary efficacy endpoint criteria in the main treatment period will be tabulated by dose level and overall. A 95% confidence interval will be calculated for the proportions using the Clopper-Pearson method. The response will be attributed to the dose level at the visit prior to the first of the two consecutive scheduled platelet counts occurred that are at least 5 days apart, see table below. A patient can have multiple responses within the same dose level and/or at different dose levels. This table will be repeated by starting dose.

Example 1: Patient had a response at 200 dose only			Example 2: Patient had a response at 200 and 400 doses.						
Visit	Dose	Platelets	Response	Dose that	Visit	Dose	Platelets	Response	Dose that
	dispensed			response is		dispensed			response is
	at this visit			attributed to		at this visit			attributed to
C1D1	200	25			C1D1	200	25		
C1D8	200	30		200	C1D8	200	30		200
C1D15	200	35		200	C1D15	200	35		200
C2D1	400	51	Υ	200	C2D1	400	51	Υ	200
C2D8	400	55		400	C2D8	400	55	Y	400
C2D15	400	42		400	C2D15	400	53		400
C3D1	600	39		400	C3D1	600	39		400
C3D8	600	40		600	C3D8	600	40		600
C3D15	600	41		600	C3D15	600	41		600
Example 3: Patient had a response at 200 and 600 doses.			Example 4: Patient had a response at 200, 400 and 600 doses.						
Visit	Dose	Platelets	Response	Dose that	Visit	Dose	Platelets	Response	Dose that
	dispensed			response is		dispensed			response is
	at this visit			attributed to		at this visit			attributed to
C1D1	200	25			C1D1	200	25		
C1D8	200	30		200	C1D8	200	30		200
C1D15	200	35		200	C1D15	200	35		200
C2D1	400	51	Υ	200	C2D1	400	51	Υ	200
C2D8	400	55		400	C2D8	400	55	Υ	400
C2D15	400	42		400	C2D15	400	53		400
C3D1	600	43		400	C3D1	600	39		400
C3D8	600	59	Υ	600	C3D8	600	59	Υ	600
C3D15	600	59		600	C3D15	600	59		600

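### Part A week counts (SAP 5.4.2.4, 5.4.2.5) pool unequal planned periods under a 24-week label, and 5.4.2.3 does not settle whether on-schedule escalators count at the lower dose

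*SAP*

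**What the plan says.** **Week counts.** Part A SAP 5.4.2.4 and 5.4.2.5 count the weeks with platelets at or above 50,000/µL and 30,000/µL over the main treatment period. Each summary is repeated for two groups: version 7.0 enrollees, described as planned for 12 weeks, and enrollees under version 8.0 or later, described as planned for 24. The tables are then repeated by starting dose.

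Other places give a different length for some of the second group:
- SAP 2.2 says amendments moved the active period from 12 to 24 weeks and then to 24 weeks or more.
- SAP 3.4.3 allows main-period cycles up to 6 under version 8.0 and up to 10 under versions 9.0 to 14.0.
- SAP Table 4, footnote 16, schedules added cycles to reach six at 400 mg BID.
- Protocol 4.8 keeps escalated patients in active treatment until 24 weeks at 400 mg BID are complete.

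**Mean change by dose level.** SAP 5.4.2.3 restricts this summary to observed values "for patients who had more than 4 weeks of study drug on that given dose level". On counting, it says "The number of weeks of study drug will be determined by number of on-study drug visits". Its one example starts from attendance at the first visit of Cycle 1 and adds that those who "did not discontinue study drug on or before data of Cycle 2 Day 1 visits will be included".

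**The concern.** A raw count of weeks depends on how many weeks a patient was planned to be observed. If a 200 mg QD starter can be followed for 36 weeks and a 400 mg BID starter for 24, the table by starting dose mixes response with length of follow-up, and the label tells the reader that the lengths are equal. SAP 5.4.2.2 recognises differing duration and adds a fixed Week 17 to 24 version. Sections 5.4.2.4 and 5.4.2.5 add none.

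In 5.4.2.3 the open question is who belongs in the lower-dose cells. Protocol 4.1 and 4.4 hold responders at their dose and let non-responders move up after 28 days. If escalators are left out, the cells below 400 mg BID keep mainly responders, so membership depends on the outcome being averaged. Two programmers could report different lower-dose means from the same data.

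Identifying a dose regimen is a Part A efficacy objective, so tables by dose level and starting dose should be readable at face value.

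**Working it through.** **1. The plan's own duration.** The protocol synopsis gives about 32 weeks per patient: 4 (screening) + 24 (treatment) + 4 (follow-up) = 32, which reproduces. It also allows up to 55 weeks for patients who need added cycles to complete 24 weeks at 400 mg BID: 55 − 8 = 47 weeks of treatment. The protocol therefore expects some main periods well beyond 24 weeks.

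**2. Planned weeks for a version 9.0+ patient who escalates every cycle.** Planned weeks = 4 × (number of lower levels) + 24.

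| Starting dose | Lower levels | Planned weeks |
|---|---|---|
| 200 mg QD | 3 | 36 |
| 400 mg QD | 2 | 32 |
| 300 mg BID | 1 | 28 |
| 400 mg BID | 0 | 24 |

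**3. Size with no dose effect.** Assumptions: the same weekly chance of a qualifying count at every dose; full retention; a non-responding cycle escalates and a responding cycle stays; six cycles at 400 mg BID once reached; at most 10 cycles. All weekly chances and responder shares below are assumed. The excess is against 400 mg BID starters, for counts at or above 50,000/µL unless stated.

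- *Independent weekly counts, chance 0.4.* A 400 mg BID starter averages 24 × 0.4 = 9.6 weeks. Simulation under the rule gives 14.0 weeks for a 200 mg QD starter (14.0/0.4 = 35 weeks of main period on average). Excess: 14.0/9.6 − 1 = 46%. With 50% retention at Week 24 it is 8.6 against 6.8 weeks (26%), and with 25% retention 5.8 against 5.1 (14%).
- *Responder types, 40% at 0.8 and 60% at 0.05.* A 400 mg BID starter averages 24 × (0.4 × 0.8 + 0.6 × 0.05) = 8.4 weeks. Excess: about 5% for 200 mg QD and 18 to 19% for 300 mg BID.
- *Steadier types, 40% at 0.95 and 60% at 0.02.* A 400 mg BID starter averages 24 × (0.4 × 0.95 + 0.6 × 0.02) = 9.4 weeks. Excess: roughly 0 to 1% for every lower starting dose.
- *Counts at or above 30,000/µL, 40% at 0.9 and 60% at 0.2.* Excess: about 13% for 200 mg QD.

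In every scenario the count over the first 24 weeks is equal across starting doses. Each excess shrinks in proportion to the share of low-dose starters enrolled under version 9.0 or later, which the documents do not give.

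**4. The on-schedule escalator in 5.4.2.3.** Section 5.3.2 sets the last date of a dose level: it "is the date of first dose of the next dose level -1". With escalation on Day 29, time at the lower dose is (29 − 1) − 1 + 1 = 28 days, exactly 4 weeks and not more.

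- *Pointing to exclusion:* Section 3.4.4 maps four visits to the old level ("200 mg QD: 1st Cycle of Exposure – Day 1, 8, 15 and 22") and Cycle 2 Day 1 to the new one.
- *Pointing to inclusion:* the example in 5.4.2.3 asks only whether study drug was stopped, and an escalator has changed dose without stopping. In 5.4.1, "The response will be attributed to the dose level at the visit prior to the first of the two consecutive scheduled platelet counts", and the tables there credit the Cycle 2 Day 1 count to the old dose, which makes a fifth visit.
- *Not decisive:* Section 3.3.1 uses "Dose level received prior to the visit for responder analyses, time-to analyses and analyses of proportion of patients meeting an endpoint". Mean change is not on that list.

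**5. What turns on it.** Let r be the share of first-cycle completers who respond at a lower dose and R their mean change, with the others unchanged (an assumption). Escalators out gives R; escalators in gives rR; the gap is (1 − r)R. For assumed r of 10 to 40% and R of 20,000 to 45,000/µL, the gap runs from 0.6 × 20,000 = 12,000 to 0.9 × 45,000 = 40,500/µL. The direction follows from the escalation rule. The size is illustrative only.

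**The case against.** **On the week counts.** The grouping is unambiguous, because it is by enrolling version, and 24 weeks is the base period. Only the label is loose. Percent of weeks at or above 50,000/µL is already planned by starting dose (5.4.2.1), as are by-cycle summaries (5.4) and individual platelet profiles marked by dose and period (5.4.1). Planned starting cohorts below 400 mg BID are at most six, so readers can look at patients one by one. The exploratory section 5.4.3 is blank in the public copy and may hold a further table. All of this limits the harm. It does not correct the label or supply a fixed window, and among the visible endpoints there is no percentage for 30,000/µL.

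**On 5.4.2.3.** The example is the only rule written for this endpoint, and it leans towards inclusion. Sections 5.3.2 and 3.4.4 were written for cumulative dose and by-visit summaries. That is fair, but the headline condition, which Protocol 10.3.2 repeats, still says otherwise for the design's ordinary non-responder.

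**Stronger readings that a reader might infer, which the documents do not support:**
- *That no dose effect implies an excess of 50, 33 and 17% (36, 32 and 28 weeks over 24).* The extra cycles of an every-cycle escalator are non-responding by rule. At a weekly chance of 0.4, a four-count cycle without two consecutive high counts averages (0.3456 + 2 × 0.1728)/0.648 = 1.07 such counts, not 1.6. For these patients the excess is 3, 2 or 1 × 1.07/9.6 = 33, 22 or 11%.
- *That a late Cycle 2 Day 1 visit decides inclusion in 5.4.2.3.* The visit window is real ("Clinic/laboratory visit windows are ± 3 days for all dosing period and lab visits"), but the section counts visits and not days.
- *That 400 mg BID is free of selection.* Higher levels receive patients who did not respond lower down, and patients needing rescue are discontinued at any level. Dose levels are not cleanly comparable under either reading.
- *That the dose choice was compromised.* Part B at 400 mg BID was added in protocol version 13.0 (March 2020), before SAP version 1.0 (November 2020).

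**Conclusion.** The point on the week counts holds. The 24-week description is wrong for version 9.0+ patients who escalate, and the by-starting-dose tables in 5.4.2.4 and 5.4.2.5 cover unequal planned periods, in a direction that favours lower starting doses. With no dose effect and full retention the excess lies between roughly 0 to 1% and about 46%. Where it falls depends mainly on assumed week-to-week stability of response, and also on retention and the version 9.0+ share. The realised size cannot be recovered from the documents.

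The point on 5.4.2.3 holds as a secondary wording conflict: the headline condition and its example give opposite answers for the on-schedule escalator, with the example leaning towards inclusion.

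Severity is minor. These are descriptive secondary summaries without hypothesis tests (SAP 3.8), partly covered by other planned tables, and the primary endpoint is unaffected.

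**What to change.** **Sections 5.4.2.4 and 5.4.2.5**
- Reword the group as 24 weeks planned, longer for version 9.0+ patients who escalate to 400 mg BID.
- In the by-starting-dose tables, add counts over a common window: the first 24 weeks for version 8.0 and later, the first 12 for version 7.0.
- Show percent of weeks beside them for 30,000/µL, as 5.4.2.1 already does for 50,000/µL.

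**Section 5.4.2.3**
- Word the visit-based example for any dose level, so that every patient who completes the first 28-day cycle at a level is included whether or not escalation follows.
- State which dose the next cycle's pre-dose Day 1 count belongs to.
- Report n in each cell. An average over the first cycle only is optional.

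**Cost.** This is SAP wording and a few tables from data already held. The Part B SAP says that the Part A report has been prepared, so supplementary tables and a statement of which reading was used in 5.4.2.3 would be enough. One limit should be stated with the new counts: within 24 weeks, low-dose starters have had less time at 400 mg BID (12 weeks for a 200 mg QD starter who escalates every cycle), so the table compares starting strategies and not doses. Early discontinuation also stays unequal, which is why the percentage belongs beside the count.
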